8.1. Adverse Events

Treatment emergent AEs (TEAEs) are defined as:

- AEs with onset at the time of or following the start of treatment with IP through final Visit or follow-up phone call.
- AEs starting prior to the start of treatment with IP but increasing in severity or relationship at the time of, or following, the start of treatment with IP through Visit 14 (End of Treatment/Follow-Up).
- AEs that occur between Visit 14 and Visit 15.

Any medical condition that is present at the time that the subject is screened will be considered as baseline and not reported as an AE. However, if the study subject's condition deteriorates at any time during the study, it will be recorded as an AE.

The Investigator will record all reportable events with start dates occurring any time after informed consent is obtained until 7 days after the last day of study participation. Events will be followed for outcome information until resolution or stabilization. Missing and partially missing start dates will be imputed for the purpose of analysis as described in Section **Error! Reference source not found.**

All AEs, TEAEs, and serious AEs (SAEs) will be coded using the MedDRA dictionary, as discussed in Section **Error! Reference source not found.**

All AE data will be categorized as Severe > Moderate > Mild. Relationship of all AEs to IP will be categorized as related or not related. In the summaries showing severity and relationship to study drug, the event with the maximum severity or strongest relationship to study drug will be reported. If a particular event is missing the severity and/or relationship, then the strongest possible severity or relationship will be assumed for analysis (severity = severe, relationship = related).

An overall summary of TEAEs will be provided; this will present number and percent of subjects who reported at least 1 of the following: TEAE (including any TEAE, TEAEs by maximum severity, and related TEAEs), TEAE leading to discontinuation of the study drug, TEAE leading to discontinuation from the study, serious TEAEs, and SAEs leading to death. TEAEs will be summarized by two time periods (TEAEs which occur prior to Visit 14 and those that occur during or after Visit 14).

In addition to the overall summary, summaries of the number and percentage of subjects with TEAEs will be displayed by overall by SOC and preferred term by time period. Summaries of TEAEs by severity (Severe > Moderate > Mild) and relationship to IP (Related > Not Related)

will also be provided. Serious TEAEs and TEAEs resulting in discontinuation of IP will be summarized separately in a similar manner.

Subject listings of AEs, SAEs, and AEs causing discontinuation of IP will be produced. Adverse events that are treatment emergent will be flagged.

The AE summary tables will include counts of subjects. Therefore, if a subject experiences more than 1 episode of a particular AE, the subject will be counted only once for that event. If a subject has more than 1 AE that is coded to the same preferred term, the subject will be counted only once for that preferred term. Similarly, if a subject has more than 1 AE within a SOC, the subject will be counted only once in that SOC. This will be handled separately for each time period (post-Visit 2 through Visit 15 [End of Treatment/Follow-up]).

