STATISTICAL METHODS	
Analysis Populations:
 
Safety population: All subjects who receive IP.
 
All analyses will be performed using the Safety population.
 
Safety Analyses:
 
Safety and tolerability implications are best addressed by applying descriptive statistical methods to the data, supplemented by calculation of confidence intervals wherever this aids interpretation. The incidence of AEs for defined periods of exposure (e.g., 3 months, 6 months, 9 months, 12 months, and overall) will be evaluated in the form of a proportion relating number of subjects experiencing events to number of subjects at risk for AEs by organ, relatedness, severity of reported AE, and by frequency of AE. In addition, frequency-type of reported AEs (once, continuous, or adaptability to treatment) by time of occurrence after Visit 2 dispensation may be tabulated. These data will be summarized and tabulated, including confidence intervals when appropriate, for descriptive purposes, and may serve as nonparametric endpoints. Time series analysis will be used where warranted to determine whether frequency of AEs changes with increased duration of exposure.
 
Efficacy Analyses:
 
Exploratory endpoints address efficacy using patient- and clinician-rated scales and will be evaluated for significant changes from baseline using a generalized linear model for repeated measures.

SAMPLE SIZE DETERMINATION	
Based on feedback from the FDA, the sample size for this study (up to 600 subjects) has been selected to attain a PH94B safety database per the ICH E1 Guideline.

STUDY AND TREATMENT DURATION	
The sequence and maximum duration of the study periods will be as follows:
 
 
1. Screening and washout (if applicable): From 7 to 35 days
 
2. 12-Month treatment period: From Visit 2 (Baseline) through Visit 14 (End of Treatment)
 
3. Follow-up period: Follow-up visit (Visit 15) conducted approximately 2 weeks after last treatment
 
 
The maximum study duration for each subject is approximately 59 weeks.
 
The maximum treatment duration for each subject is 12 months.

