Subjects will be instructed to return to the clinic for Visit 3 after 30 days ( $\pm 3$  days). At Visit 3, subjects will undergo clinical laboratory assessments (clinical chemistry, hematology, urinalysis, pregnancy test, and urine drug screening), vital signs, 12-lead ECG, physical examination (limited to nasal passage and oropharynx examination unless any AEs are reported), HAM-D17, [REDACTED] LSAS, C-SSRS, CGI-S, CGI-I, and self-evaluation by the patient-reported outcome measure, Patient Global Impression of Change (PGI-C). At Visit 3, PH94B use and any daily reports of health problems that have been recorded in the eDiary application will be reviewed and AEs and concomitant medications will be reported and recorded. Subjects will receive a 1-month supply of PH94B.

Subjects will return to the clinic at monthly intervals ( $\pm 7$  days, Visits 4 to 13), and will repeat the same assessments as those performed at Visit 3. PH94B use and any daily reports of health problems that have been recorded in the eDiary application will be reviewed, AEs and concomitant medications will be reported and recorded at each visit. Subjects will receive a 1-month supply of PH94B at each monthly visit.

At Visit 14 (12 months $\pm$ 2 weeks), treatment will conclude, and subjects will undergo clinical laboratory assessments (clinical chemistry, hematology, urinalysis, pregnancy test, and urine drug screening), vital signs, 12-lead ECG, physical examination, HAM-D17, [REDACTED] LSAS, C-SSRS CGI-S, CGI-I, PGI-C, and the Penn Physician Withdrawal Checklist (PWC-20). Also, PH94B use and any daily reports of health problems that have been recorded in the eDiary application will be reviewed, and AEs and concomitant medications will be recorded and reported. Subjects will also be informed of their follow-up visit (Visit 15).

Subjects will return to the clinic for a follow-up visit (Visit 15, 54 weeks  $\pm$ 3 days), approximately 2 weeks after the last PH94B administration, to undergo C-SSRS, PWC-20, and vital signs assessments, and record AEs.

Subjects who discontinue study treatment without completing 12 months of treatment will attend an Early Termination Visit (Visit 14) as soon as possible after discontinuing treatment, and return to the clinic for a follow-up visit (Visit 15) approximately 2 weeks later.

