If a subject is withdrawn before completing the study, the reason for withdrawal and the date of discontinuation will be recorded on the appropriate page of the electronic case report form (eCRF).

All attempts will be made to have subjects return to the clinic to complete the assessments or procedures performed at the Early Termination visit (see Section 10.2.3) in the event of early withdrawal after Visit 2 or any visit other than Visit 14 after IP administration. All attempts to contact the subject, including phone or email, must be recorded in the source documents. Data will be collected from subjects on treatment only.

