#### **8.4. Subject Replacement Criteria**

Withdrawn subjects will not be replaced. If a substantial number of subjects are withdrawn from the study, the sponsor will evaluate the need for developing replacement criteria. Rescreening will be permitted on a case-by-case basis after discussion with the medical monitor.

The subject number for a withdrawn subject will not be reassigned to another subject.

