3.1. Overall Design

3.2. Sample Size and Power

Based on feedback from the FDA, the sample size for this study (up to 600 subjects) has been selected to attain a PH94B safety database per the ICH E1 Guideline.

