4.1. Introduction

Data processing, tabulation of descriptive statistics, calculation of inferential statistics, and graphical representations will primarily use SAS (release 9.4 or higher). If the use of other software is warranted, the final statistical methodology report will detail what software was used for what purposes.

Continuous (quantitative) variable summaries will include the number of subjects (n) with non-missing values, mean, standard deviation (SD), minimum, and maximum.

Categorical (qualitative) variable summaries will include the frequency and percentage of subjects who are in the particular category or each possible value. In general, the denominator for the percentage calculation will be based upon the total number of subjects in the study population with non-missing values.

The minimum and maximum will be reported with the same degree of precision (ie, the same number of decimal places) as the observed data. Measures of location (mean and median) will be reported to 1 degree of precision more than the observed data and measures of spread (SD) will be reported to 2 degrees of precision more than the observed data.

Percentages <100% will be presented to 1 decimal place and percentages of 100% will be reported with no decimal place. Counts of zero will be presented without percentages.

Unless otherwise indicated, all statistical tests will be conducted at the 0.05 significance level using 2-tailed tests, and *P* values will be reported. Corresponding 95% confidence intervals (CIs) will be presented for statistical tests. The statistical tests will be descriptive with no adjustment for multiplicity.

This study is considered an exploratory study. Statistical tests will be interpreted in an exploratory sense only and will not be considered formal hypothesis tests.

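### The TEAE tables specified in SAP 8.1 are crude percentages, and the protocol's at-risk incidence by exposure period is left out without being recorded as a change

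*SAP*

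**What the plan says.** **SAP.** The overall TEAE summary in Section 8.1 is specified so that "this will present number and percent of subjects who reported at least 1 of the following". The tables by system organ class, preferred term, severity and relationship count each subject once and also give number and percentage. The time split has two parts: "TEAEs which occur prior to Visit 14 and those that occur during or after Visit 14". Section 4.1 sets the general denominator: in general, "the denominator for the percentage calculation will be based upon the total number of subjects in the study population with non-missing values". Section 8 bases all safety reporting on the Safety population. The AE table list in Section 12.3 has no person-time rate, no time-to-first-event estimate and no table by exposure interval. Section 7.4 summarises days of exposure separately and overall.

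**Provisions that go further.** Protocol 13.1.4 (also the synopsis) plans AE incidence for periods such as 3, 6, 9 and 12 months and overall. It divides by subjects at risk, or exposed in the period, with confidence intervals when appropriate and possible time series analysis. SAP Section 5 says AEs will be grouped by length of exposure and level of use.

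**Follow-up.** The synopsis says: "The maximum treatment duration for each subject is 12 months". Withdrawal is free at any time, and Protocol 8.4 states: "Withdrawn subjects will not be replaced". Protocol 8.3 adds: "Data will be collected from subjects on treatment only". Protocol 7.1 has early leavers attend Visit 14 as an early termination visit and Visit 15 about 2 weeks later.

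**The concern.** Safety over up to 12 months is the primary objective, and by SAP 3.2 "the sample size for this study (up to 600 subjects) has been selected to attain a PH94B safety database". Readers of a long-term safety database will tend to take its AE percentages as one-year risks, or set them beside studies of other length or retention. A subject who leaves event-free after one month stays in the denominator like one observed for a year. If many leave early, the percentage is lower than the one-year risk, which is the reassuring direction. Late-onset effects, the ones a 12-month study is best placed to find, are affected most. The protocol had a remedy in its at-risk denominators. The SAP's AE section does not carry it over.

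**Working it through.** **1. The plan's own figure.** The sample size of up to 600 rests on the ICH E1 guideline, with no event rate, dropout rate or precision target. There is no calculation to reproduce.

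**2. Is the omission recorded?** SAP Section 10 lists the removal of the interim safety analysis and of the eDiary-based use objectives. It also says categorical data were reviewed qualitatively instead of assessing change in proportion over time. That last entry uses the language of the CGI-S, CGI-I and PGI-C endpoints and does not mention AEs. Nothing in Section 10 refers to the incidence by exposure period in Protocol 13.1.4.

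**3. Size under constant hazards.** Assumed inputs, because the documents give neither: true 12-month risk R and 12-month dropout D, with dropout independent of AEs. Let L = -ln(1 - R) and M = -ln(1 - D). Then

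crude = L/(L + M) x [1 - exp(-(L + M))], where exp(-(L + M)) = (1 - R)(1 - D).

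For R = 30%, L = 0.3567.
- D = 20%: M = 0.2231; crude = 0.3567/0.5798 x (1 - 0.56) = 27.1%.
- D = 50%: M = 0.6931; crude = 0.3567/1.0498 x (1 - 0.35) = 22.1%.

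| D | R = 30% reads | R = 10% reads |
|---|---|---|
| 10% | 28.6% | 9.5% |
| 20% | 27.1% | 9.0% |
| 30% | 25.5% | 8.4% |
| 40% | 23.9% | 7.9% |
| 50% | 22.1% | 7.3% |

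The relative shortfall is about 5% at 10% dropout, 10% at 20% and 26-27% at 50%. Spreading dropout evenly over the year changes little: a 30% risk then reads 27.2% at 20% dropout and 24.4% at 40%.

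**4. Size when onset timing varies, with R = 30% and D = 50%.**
- All AE hazard in month 1: 12L/(12L + M) x [1 - exp(-(12L + M)/12)] = 4.280/4.973 x 0.3393 = 29.2%. Shortfall (30 - 29.2)/30, about 3%.
- All AE hazard in months 7-12: exp(-M/2) x 2L/(2L + M) x [1 - exp(-(2L + M)/2)] = 0.7071 x 0.5072 x 0.5050 = 18.1%. Shortfall (30 - 18.1)/30, about 40%.

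Timing therefore matters as much as dropout.

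**5. Does a person-time rate help?** In the constant-hazard case with D = 50%, time at risk per subject is 0.65/1.0498 = 0.619 years. The rate is 0.2208/0.619 = 0.357 per year, and 1 - exp(-0.357) returns 30%. The conversion is exact only under a constant hazard.

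**The case against.** **The SAP never calls n (%) a 12-month risk.** This stands. Safety is descriptive and the percentage is a correct observed frequency. A reader might infer that the SAP's AE percentages are wrong. They are not; the shortfall arises only when they are read as one-year risk. If the target is instead the chance of an event before discontinuation, the crude percentage is already close to it.

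**The plan does provide for exposure.** A reader might infer that crude percentages are all that was ever planned, with no AE confidence intervals. Protocol 13.1.4 and SAP Section 5 contradict that. The defect is that SAP 8.1 and its table list do not carry these provisions out and Section 10 does not say so. The SAP contents also announce table shells that are not in the available text, and a denominator could be fixed there.

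**Dropout alone does not set the size.** This stands, as step 4 shows. A reader might take the protocol's counts of about 300 subjects at 6 months and 100 at 12 months as a retention forecast from 600. They are the trigger for an interim analysis since removed, not a dropout assumption.

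**The Visit 14 column.** A reader might infer that the at/after-Visit-14 percentage is certainly diluted. Its denominator is not stated: all Safety subjects follows only from a rule that applies in general. Early leavers who attend Visits 14 and 15 do enter that period. No figure for dilution can be supported.

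**The remedies have assumptions.** Kaplan-Meier needs non-informative censoring, which is doubtful if tolerability drives withdrawal. Dosing is as needed and SAP Section 10 calls the eDiary data unreliable, so person-years are follow-up time, not drug exposure. SAP 6.1.8 imputes partial onset dates early, which shifts time-to-event estimates. These points shape the fix without removing the need for it.

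**Conclusion.** The point holds as a cheap improvement. SAP 8.1 and its table list specify TEAEs as crude n (%) in two periods. They leave out the protocol's at-risk incidence and the SAP's own grouping by length of exposure, and Section 10 does not record this. Under non-informative dropout the crude percentage lies below 12-month risk whenever subjects leave early. The amount depends on both dropout and AE timing, and the documents fix neither, so only the assumed range in the working can be given. Early local reactions would be barely affected; late-onset events could be understated substantially.

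**What to change.** Keep n (%), and amend SAP 8.1 and the table list as follows.

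1. Restore the Protocol 13.1.4 incidence by 3-month interval, showing the number at risk. Protocol 13.1.3 already defines suitable intervals for exposure (0-3, 4-6, 7-9 and 10-12 months). If it is not restored, record and justify the omission in Section 10.
2. For any, related, severe and serious TEAEs, TEAEs leading to discontinuation, and the most frequent preferred terms, add:
   - first-event rates per 100 person-years of follow-up, with exact 95% CI;
   - cumulative incidence at 6 and 12 months with 95% CI. Use Kaplan-Meier for risk under continued follow-up, or Aalen-Johansen if discontinuation is treated as competing. The latter answers a different question and will lie close to n (%), so name the target.
3. State that the at/after-Visit-14 denominator is the subjects who entered that period.
4. Base any statement about 12-month risk on the cumulative incidence, and state the non-informative censoring assumption where Kaplan-Meier is used. Describe person-years as follow-up time, not drug exposure.

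The cost is SAP wording and extra table columns. AE onset and visit dates are already collected. The sponsor takes on a censoring assumption to state and defend, and reported AE risk may look somewhat less favourable.

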9.	An acute or chronic condition, including an infectious illness, uncontrolled seasonal allergies at the time of the study, or significant nasal congestion that potentially could affect drug delivery to the nasal chemosensory epithelium.
10.	Any current clinically significant and/or uncontrolled medical condition, based on medical history or as evidenced in screening assessments, such as COVID-19, HIV, cancer, stroke, congestive heart failure, uncontrolled diabetes mellitus, or any other medical condition or disease that, in the clinical judgment of the Investigator, could

	
place the subject at undue risk, interfere with study participation, or confound the results of the study.
 
 
11. Women who have a positive urine pregnancy test prior to IP administration. Women who are currently breastfeeding are not eligible.
 
12. History of cancer or malignant tumor not in remission for at least 2 years. Basal cell skin cancers are not exclusionary.
 
13. Subjects with clinically significant abnormalities in hematology, blood chemistry, urinalysis, 12-lead ECG, or physical examination identified at study entry or during the legacy study which, in the clinical judgment of the Investigator, could place the subject at undue risk, interfere with study participation, or confound the results of the study.
 

TEST PRODUCT	
Name: PH94B Nasal Spray
 
Dose, route, frequency: 3.2 µg administered as an intranasal (i.n.) solution (a 1.6-µg spray to each nostril per dose), up to 4 times a day.

CONTROL PRODUCT	
Not applicable

TREATMENT REGIMENS	
Treatment will be administered as needed at 3.2 µg per dose of PH94B (<math>\leq</math> 4 doses per day) from Visit 2 (Baseline) to Visit 14 (End of Treatment).
 
Treatment with PH94B should be self-administered as needed approximately 15 minutes prior to or during an anxiety-provoking social situation or event. Consecutive nasal administrations of IP should be [REDACTED], with no more than 4 administrations per day. Treatment does not need to be administered every day.

PLANNED STUDY SITES	
The study is designed as a multicenter study conducted in the USA with approximately 40 clinical study sites.

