- c Physical examination will include measurement of weight and an examination of the nasal passages. Height will be measured at Screening and at Visit 14. The physical examinations done at Visit 1, Visit 2 and Visit 14 will be comprehensive. The physical examinations done at Visit 3 to Visit 13 will be focused but must include examination of the nasal passages and oropharynx. Other organ systems should be examined at Visit 3 to Visit 13 if the subject reports AEs or if the investigator has specific concerns.
- d [REDACTED].
- e 12-Lead electrocardiograms will be administered in a supine position after the subject has rested for 5 minutes.
- f For all subjects, a review of inclusion and exclusion criteria will be conducted at Visit 2 to confirm eligibility.

Note: Long-term C-SSRS will be administered at screening. All other C-SSRS evaluations will be "Since Last Visit."

Note: If central laboratory urine drug screen testing is positive for a subject [REDACTED], then the participation of the subject in the study may have to be discontinued. The Medical Monitor should be consulted on these cases. An unscheduled repeat urine drug screen may be obtained to investigate whether drug use is continuing.

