Subjects will be instructed to return to the clinic for Visit 3 after 30 days (± 3 days). At Visit 3, subjects will undergo clinical laboratory assessments (clinical chemistry, hematology, urinalysis, pregnancy test, and urine drug screening), vital signs, 12-lead ECG, physical examination, HAM-D17, [REDACTED] LSAS, C-SSRS, CGI-S, CGI-I, and self-evaluation by the patient-reported outcome measure, Patient Global Impression of Change (PGI-C). At Visit 3, PH94B use recorded in the eDiary application will be reviewed and AEs and concomitant medications will be reported and recorded. Subjects will receive a 1-month supply of PH94B (6 vials).

Subjects will return to the clinic at monthly intervals (± 7 days, Visits 4 to 13), and will repeat the same assessments as those performed at Visit 3. PH94B use recorded in the eDiary application will be reviewed, AEs and concomitant medications will be reported and recorded, and at each Visit subjects will receive a 1-month supply of PH94B (6 vials).

At Visit 14 (1 year ± 2 weeks), treatment will conclude, and subjects will undergo clinical laboratory assessments (clinical chemistry, hematology, urinalysis, pregnancy test, and urine drug screening), vital signs, 12-lead ECG, physical examination, HAM-D17, [REDACTED] LSAS, C-SSRS CGI-S, CGI-I, and PGI-C. Also, PH94B use recorded in the eDiary application will be reviewed, and AEs and concomitant medications will be recorded and reported. Subjects will also be informed of their follow-up Visit (Visit 15).

Subjects will return to the clinic for a follow-up Visit (Visit 15, 54 weeks ± 3 days), approximately 2 weeks after the last PH94B administration, to undergo C-SSRS and vital signs assessments, and record AEs.

Safety Considerations:

Safety and tolerability of PH94B (≤ 4 doses per day up to 12 months in up to 600 subjects) will be assessed and summarized through changes from baseline (Visit 2) to end of treatment (Visit 14) in AEs, laboratory values, 12-lead ECGs, physical examinations, and vital sign assessments following exposure to PH94B.

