6.1.7. Derived Variables

6.1.7.1. General

- **Age** = Integer difference in years between the subject's date of informed consent and date of birth.
- **Change from Baseline to Visit X in Parameter Y** = Value at Visit X minus the value at Baseline (as defined in Table 2).
- **Percent Change from Baseline to Visit X in Parameter Y** = Change from Baseline to Visit X in Parameter Y divided by the value at Baseline (as defined in Table 2) multiplied by 100.
- **Shift from Baseline to Visit X in Parameter Y Categories** = Cross-tabulation of below the lower limit of the normal range, within the limits of the normal range, and above the upper limit of the normal range at Baseline (as defined in Table 2) versus at Visit X.
- **Height (cm) and Weight (kg)** = Height (cm) will be calculated as height (in) times 2.54. Weight (kg) will be calculated as weight (lb) times 0.4536.
- **Temperature (C°)** = Temperature (F°) -32 times 5 divided by 9.
- **Treatment duration** = Days in study (date of last Visit minus date of Visit 2 (Baseline)).
- **Days of exposure** = Date of Visit 14 (End of Treatment) minus date of Visit 2. [In the case Visit 14 is missing then the date of study completion will be used.]
- **PH94B use** = average weight of all 6 vials when dispensed – weight of all 6 vials when returned at subsequent visit, at each visit.

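### SAP 8.1 divides treatment-emergent adverse events at Visit 14 instead of at end of treatment, so the by-period tables can misplace events in both directions

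*SAP*

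**What the plan says.** SAP 8.1 gives the reporting rule: "TEAEs will be summarized by two time periods (TEAEs which occur prior to Visit 14 and those that occur during or after Visit 14"). The next paragraph of 8.1 carries the split into the main tables, which are to be "displayed by overall by SOC and preferred term by time period". Serious events and events leading to discontinuation follow in similar fashion.

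On what Visit 14 is, the documents agree. Protocol 2.1 has treatment given "from Visit 2 (Baseline) to Visit 14 (End of Treatment"). SAP section 3 says "At Visit 14 (1 year ± 2 weeks), treatment will conclude", and protocol 7.1 says that at this visit "treatment will conclude, and subjects will undergo clinical laboratory assessments". SAP 6.1.7.1 defines days of exposure as "Date of Visit 14 (End of Treatment) minus date of Visit 2", and SAP 7.4 repeats this.

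On examinations, footnote c of protocol 2.2 says "The physical examinations done at Visit 1, Visit 2 and Visit 14 will be comprehensive"; those at Visits 3 to 13 are focused.

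On early stopping, protocol 7.1 has the ET visit, which is also numbered Visit 14, take place as soon as possible after treatment is discontinued.

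On percentages, SAP 4.1 says that in general "the denominator for the percentage calculation will be based upon the total number of subjects in the study population with non-missing values". Protocol 13.1.4 instead relates events to subjects at risk and to those exposed during the period.

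**The concern.** Splitting AEs at the end of treatment has one evident use: to let a reader compare events on PH94B with events after stopping. The boundary chosen does not make that comparison. It is a visit, and it places the visit itself on the later side. A completer's Visit 14 date thus counts towards exposure in the exposure table but falls in the follow-up period of the AE tables. For someone who had already stopped, the days before the ET visit fall in the earlier period.

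Long-term safety is the primary objective and AEs are the primary outcome, so these are the main tables of the study. The short second period is the most exposed, because it holds few events and a few misplaced ones change its appearance.

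**Working it through.** The plan gives no figure to reproduce. The check sets the rule against the visit schedule.

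**1. Completers.** Treatment runs from Visit 2 to Visit 14 (protocol 2.1), and exposure is counted to the Visit 14 date (SAP 6.1.7.1, 7.4). Under SAP 8.1 an AE with onset that day goes to the second period. The third bullet of the treatment-emergent definition in the same section describes the follow-up interval differently, as lying between Visits 14 and 15.

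**2. What Visit 14 contributes.** Visit 15 has vital signs, C-SSRS, PWC-20 and AE review only (protocol 10.2.4). For completers, any second-period AE found by a scheduled laboratory test, ECG or physical examination must therefore come from Visit 14.

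- Post-baseline treatment-period visits: Visits 3 to 14, so 14 − 3 + 1 = 12.
- Share placed in the second period: 1/12 = 8.3%.
- Scheduled comprehensive post-baseline examinations: Visit 14 only, so 1 of 1.

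The SAP's published table list (12.3, 12.4) shows no physical-examination summary, although protocol 13.1.4.6 plans one; only Listing 16.2.9.3 appears. The table numbering skips 14.3.6.3, so this is what is visible rather than proof of absence. On the visible list, a Visit 14 examination finding reaches a summary table only as an AE.

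**3. Early terminators.** Suppose last dose, then AE onset, then ET visit, in that order. The AE precedes Visit 14/ET and is placed in the first period, although treatment had stopped. The ET findings themselves fall in the second period, which is right for this subject. If discontinuation is decided at a scheduled visit and the ET assessments are done there (protocol 10.2.3), the subject resembles a completer. Subjects with no Visit 14/ET have no boundary: SAP 6.1.7.1 substitutes the completion date for exposure, but 8.1 has no such fallback.

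**4. Why the second period bears most of it.** It runs nominally from week 52 to week 54, about 2 weeks. As an illustration only, assume a constant AE rate, full completion and follow-up, 10% to 50% of AEs found by test or examination evenly across the 12 visits, and each dated to the visit that found it.

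- Post-treatment events per 100 on-treatment events: 100 × 2/52 = 3.85.
- Events moved: 100 × 0.10/12 = 0.83 to 100 × 0.50/12 = 4.17.
- First period loses 0.8% to 4.2%.
- Second period gains 0.83/3.85 = 22% to 4.17/3.85 = 108%.

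None of these rates is in the documents. The lines show the leverage of a short period and are not an estimate.

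**5. Denominator.** If the second-period percentage used the whole Safety population while a fraction p was followed, the percentage among those followed would be 1/p times as large: 1/0.90 = 1.1 at 90% follow-up and 1/0.50 = 2.0 at 50%. Both fractions are assumptions.

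**The case against.** A reader might infer that findings from the last on-treatment assessments are reported as off-drug events. The documents do not support that. The SAP labels the period only by reference to Visit 14, and every such event remains treatment-emergent in the overall summary. Only findings logged as AEs are affected (protocol 13.1.4), and laboratory, vital-sign and ECG values are summarised by visit regardless (SAP 8.2 to 8.4). Protocol 11.2.3 records when an AE first occurred, so symptoms that began earlier and were merely reported at Visit 14 belong to the first period, provided that occurrence in SAP 8.1 means onset, which it does not define.

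A reader might also infer that the on-treatment rate is materially understated, or that the second-period percentages are certainly diluted by people never followed. Neither is established. Even the illustration takes only a small share from the first period, and counting each subject once per term could shrink it further. The denominator reading rests on a general rule in SAP 4.1 that speaks of non-missing values, and the AE table shells are not in the available text.

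Finally, withdrawal has its own instrument, the PWC-20 at Visits 14 and 15, and the safety analysis is descriptive.

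These points limit the consequence. They leave the boundary itself undefended: it disagrees with the SAP's own exposure definition for completers and errs the other way for those who stopped early.

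**Conclusion.** The point holds as a defect in the period definition. The rule is explicit and applies to the main AE tables. It pools a completer's Visit 14-onset events with follow-up events, and counts an early terminator's events between stopping and Visit 14/ET with those before Visit 14. The effect is confined to the by-period AE tables and falls mainly on the second period. Overall treatment-emergent totals are untouched.

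Its structural size is 1 of 12 treatment-period visits and the single scheduled comprehensive post-baseline examination. The number of events, and the net direction across completers and early terminators together, cannot be computed from the documents.

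The conclusion rests on two readings: that occurrence means onset, and that the Visit 14 date closes exposure for completers, as the SAP defines it. Dosing is as needed, so a completer's actual last dose may be earlier. The denominator is a matter to specify, not a demonstrated error. The change should be made because these are primary safety tables and it is cheap.

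**What to change.** In SAP 8.1, replace the visit boundary with an end-of-treatment date.

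- **End of treatment:** the Visit 14 date for completers; the last-dose date, or the discontinuation date recorded in the eCRF (protocol 8.3), for early terminators. State which takes precedence and whether the recorded date refers to treatment or to the study, since SAP section 10 calls the eDiary data unreliable.
- **On-treatment:** onset on or before that date, and any abnormality first detected at a completer's Visit 14 assessment, even if the result arrives later.
- **Post-treatment:** later onset, up to Visit 15.
- **Denominator for post-treatment percentages:** subjects followed in that period, in line with the at-risk wording of protocol 13.1.4, instead of the whole Safety population.
- **Consistency:** use the same periods in SAP section 5 and in 8.1, 8.1.1 and 8.1.2. Section 5 now groups AEs by length of exposure and level of use, the end of 8.1 runs from after Visit 2 through Visit 15, and 8.1.1 and 8.1.2 each describe the periods in other terms.

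Moving the boundary to include Visit 14/ET for everyone would be simpler but wrong for early terminators: it would add ET findings in subjects already off treatment to the on-treatment column.

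The cost is a few lines in those sections and the matching lines of the AE shells, with no new data collection if the recorded discontinuation date is used. The downside is small: a true post-treatment AE starting on the end-of-treatment date would count as on-treatment.
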